2.1 Background Information and Relevant Literature

Distance learning. The Division of Dental Medicine within the Hansjörg Wyss Department of Plastic Surgery at the NYU School of Medicine has developed ground-breaking initiatives in order to connect remote sites and programs for didactic training. With the assistance of an “Innovative” grant from the Health Resources and Services Administration (HRSA) awarded over a decade ago to introduce a live, interactive, video-teleconferencing (VTC) system, a distance learning component was added to the NYU Langone

CONFIDENTIAL

This material is the property of the NYU School of Medicine and Langone Medical Center. Do not disclose or use except as authorized in writing by the study sponsor
Interventional Template Version: 05 JAN 2017

Dental Medicine residency training program. This enabled the NYU Langone Dental Medicine network to develop clusters of training sites geographically removed from the primary teaching facilities at FHC in Brooklyn, NY, thus ensuring educational equity across geography.

In addition to the traditionally low-income, racial/ethnic minority, and immigrant patient populations of community health centers (CHCs), the Division of Dental Medicine places dental residents in Indian Health Service facilities as well as other ambulatory care organizations, thus providing care to socioeconomically underserved communities in both urban and rural areas. This pioneering distance learning system has enabled its hospital-based dental residency program to have a complete electronically-mediated curriculum as part of the didactic training program, in addition to clinical experiences at each specific training site. Currently, distance learning is delivered through both synchronous (e.g., live interactive video teleconferencing) and asynchronous (e.g., on-line educational modules) methodologies.

Tele-dentistry. Dental provider shortages, remoteness, funding challenges, and decreased costs, coupled with advances in technology, have increased interest in the use of tele-medicine applications.³ In recent years, there have been extensive technological innovations in the field of dentistry. Among the most important of these advances are the use of computers, tele-communications technology, digital diagnostic imaging services, and specialized hardware and software for patient screening and follow-up. Technological capabilities that were considered out of reach 20 years ago are now possible in dental care, but implementing and evaluating them in diverse, low-resource dental settings requires the engagement of key organizational stakeholders and clinical, technological, and scientific experts.

By exploiting advanced information technologies, the science of dentistry has unprecedented potential to progress far more than it has during the previous 20 centuries. New information technologies have not only improved the quality of dental patient management, but have also made it possible to achieve partial or complete management remotely, even at distances of thousands of miles from health care centers or dental experts. Networking, the sharing of digital dentistry information, and distant consultations, workups, and analyses are handled by a specific branch of dentistry-related tele-medicine known as tele-dentistry.^{4,5}

Cancer risks in low-income, racial/ethnic minority, and immigrant communities. Cancer risks are compounded in low-income, racial/ethnic minority, and immigrant communities by difficulties in accessing health care services and multiple linguistic, cultural, economic, and social barriers. Acculturation also plays a key role in health status and promotion, as immigrants who have lived in the United States for longer periods of time and possess higher degrees of acculturation may have different lifestyles than those who report fewer years of US residence or lesser degrees of acculturation.^{6,7} For all population groups, cultural beliefs influence both health care choices and service use. For instance, among certain Asian subgroups, a strong sense of group collectivism exists, and individuality is submerged in the interest of group welfare.⁸ Friends, neighbors, and family members are often accessed and consulted before turning to formal health care services,⁸ which may delay the identification and diagnosis of oral lesions, especially in remote CHCs which often lack oral pathology expertise.

2.2 Diagnostic-imaging multiformat camera

The SOPROCARE is intended for clinical practice of general dentistry, as an aid in the diagnosis of pit and fissure caries, as an aid to highlight dental plaque and gingival inflammations (restricted to gingival inflammations which lead to bleeding upon probing) and as intra-oral camera to visualize anatomical details that are invisible to the naked eye or with a mirror (thanks to its magnification). In CARIO mode, the camera helps the dental practitioner to highlight carious warning on pits and fissures of the occlusal side of the teeth. In DAYLIGHT mode, the camera enables you to visualize anatomical details invisible to the naked eye or with a mirror (thanks to its magnification). In PERIO mode, the camera helps the dental practitioner to see the presence of dental plaque but also to highlight gingival inflammations (restricted to gingival inflammations which lead to bleeding upon probing). This mode offers to the dentist and/or hygienist a tool

CONFIDENTIAL

This material is the property of the NYU School of Medicine and Langone Medical Center. Do not disclose or use except as authorized in writing by the study sponsor

Interventional Template Version: 28 APR 2017

for an improved communication, motivation and education of his/her patients, who will then become aware of their oral health condition.

This medical device is classified IIb according to the current applicable European Directive. It is CE marked. Notified Body: CE 0459 LNE-GMED. This medical device dedicated to dental cares is restricted to health staff; it is not reimbursed by health insurance organizations. This device was developed and manufactured according to the EN ISO 13485 quality control certification system. Read carefully the user manual. Manufacturer: SOPRO (France).

2.2.1 Preclinical Data

N/A

2.2.2 Clinical Data to Date

N/A

2.3 Rationale

Even as each preventive dental visit includes a screen for oral cancer, detection and identification of lesions is hampered by difficulty in visualizing lesions intraorally and lack of expertise among general dentists in oral cancer detection. We hypothesize that the oral pathology asynchronous tele-mentoring pilot project will both feasible to implement in the dental clinic setting, and acceptable to patients.

2.4 Potential Risks & Benefits

2.4.1 Known Potential Risks

The proposed study poses minimal risk to subjects. Loss of confidentiality is the greatest potential risk to study subjects. All data entered into the research databases (in REDCap) will be protected by confidential entry codes. Locked file cabinets will be used to store materials with identifying information (e.g., consent forms). Unique identifiers will always replace patient names in all research databases. All computer systems are protected from possible external access. No Internet access is possible with the research systems to be used for this study. In addition, computer records will be maintained in such a way that the patient's name or other obvious identifying information is not accessible in the same file or by using the same code. Once digital recordings are transcribed and entered into a password-protected database, the recordings will be deleted from the study files. Interview subjects will have the right to refuse to participate without any compromise of their employment status, reputation, or professional relationships. Records of subjects will not be linked to employment records. Also, if a subject is uncomfortable during any interview situation, s/he may stop the interview at any time without penalty. The data collected for this study will be used strictly for the purposes stated in this application and will only be available to NYU Langone Health research staff.

2.4.2 Known Potential Benefits

By participating in the proposed research, research subjects may gain the benefit of augmented services to prevent and/or identify oral cancer. Some patients may individually experience no benefit. This study will yield knowledge regarding methods for increasing adherence to evidence-based guidelines for prevention of, screening for, and treatment of oral cancer. Overall, the benefits of understanding effective methods for helping patients reduce their risk of oral cancer far outweigh the remote possibility of a breach of confidentiality.

CONFIDENTIAL

This material is the property of the NYU School of Medicine and Langone Medical Center. Do not disclose or use except as authorized in writing by the study sponsor

Interventional Template Version: 28 APR 2017

3 Objectives and Purpose

The purpose of the proposed research project is to evaluate and enhance the feasibility and acceptability of integrating a tele-mentoring component into the identification of oral lesions at the 6 dental clinics of Family Health Centers at NYU Langone (FHC), a Federally Qualified Health Center (FQHC) in Brooklyn, NY.

The tele-mentoring intervention involves training dental faculty member subjects and resident subjects to use intraoral cameras to take photographs of oral lesions and place them in the Dentrix electronic health record (EHR), along with descriptions of the lesions. This information will then be sent via Dentrix EHR to [name], the Director of Oral Pathology at NYU Langone Hospital – Brooklyn, and an initial dummy code entry will be placed in the Dentrix EHR. For each patient with a detected lesion, [name] will then review the Dentrix EHR chart and the uploaded photograph(s) of the lesion(s) found and place his observations in the Dentrix EHR. Next, [name] will discuss his findings with the involved dental faculty member / dental resident via secure NYU Langone Health e-mail. The dental provider will then enter an apt comment in the Dentrix EHR, using the following template: “Reviewed entry and contacted patient. Follow-up appointment needed / not needed (+ date) for an appointment on (date).” A second dummy code entry will then be placed in the patient chart in the Dentrix EHR. Once a week, [name] will receive a Dentrix EHR report with the 2 affiliated dummy codes for the tele-mentoring pilot study, and assure that entries for both codes are entered, and the loop is closed.

Using a mixed-methods approach, we will evaluate and enhance the feasibility and acceptability of integrating a tele-mentoring component into the identification of oral lesions at the 6 FHC dental clinics. This will be achieved through:

1. Administering provider surveys (n=12) that consist of a checklist of 10 key components of the intervention based on process, and asking the dental provider subjects at each of the 6 FHC dental sites if each one was covered.
2. Conducting semi-structured interviews (n=6) with dental resident subjects at each of the 6 FHC sites to assess specific barriers to sustaining the intervention and strategies for addressing these barriers to facilitate integration of the intervention into the routine workflow of the dental clinics. The interviews will be informed by the Consolidated Framework for Implementation Research (CFIR)¹ and the Implementation Outcomes Framework (IOF).²
3. Administering brief exit interviews (n=30) with patient subjects at each of the 6 FHC dental sites regarding the acceptability of the intervention. The survey will assess patient satisfaction with the use of intraoral cameras at chairside to screen for and refer patients with oral lesions and identification of these oral lesions via tele-mentoring with an oral pathology expert ([name]).

Impact: If this pilot study proves successful, NYU Langone Health is well-equipped with both teaching and organizational expertise in faculty development activities, as well as the existing NYU Langone Dental Medicine national network of video-teleconferencing and web-based educational technology, to scale-up the proposed oral pathology asynchronous tele-mentoring educational program for the teaching of dental educators and residents, with the ultimate goal of improving patient care.

3.1 Primary Objective

To assess the feasibility of the oral pathology asynchronous tele-mentoring intervention in the dental clinic setting.

3.2 Secondary Objectives (if applicable)

To assess the acceptability of the asynchronous tele-mentoring pilot intervention to adult dental patients.

CONFIDENTIAL

This material is the property of the NYU School of Medicine and Langone Medical Center. Do not disclose or use except as authorized in writing by the study sponsor
Interventional Template Version: 28 APR 2017

4 Study Design and Endpoints

4.1 Description of Study Design

This one-year pilot study is composed of 2 parts:

- During months 1-6, we will complete the installation of the intraoral cameras in the dental operatories at FHC and design the Dentrix EHR screens for entering the information and tracking the involved steps of the tele-mentoring intervention. Dentist and resident subjects at all 6 FHC dental sites will then be trained by [name] and [name] to use the intraoral cameras to take photographs of oral lesions and place them in the Dentrix EHR, along with descriptions of the lesions.
- During months 6-12, dentist and resident subjects will begin screening eligible patients for oral lesions and place photographs and descriptions of any found lesions in the Dentrix EHR, along with an initial dummy code entry. For each patient with a detected lesion, [name] will then review the Dentrix EHR chart and the uploaded photograph(s) of any lesion(s) found and place his observations in the Dentrix EHR. Next, [name] will discuss his findings with the involved dental faculty member / dental resident via secure NYU Langone Health e-mail. The dental provider will then enter an apt comment in the Dentrix EHR, using the following template: "Reviewed entry and contacted patient. Follow-up appointment needed / not needed (+ date) for an appointment on (date)." A second dummy code entry will then be placed in the patient chart in the Dentrix EHR. Once a week, [name] will receive a Dentrix EHR report with the 2 affiliated dummy code entries for the tele-mentoring pilot study, thus assuring that entries are made for both codes, and the loop is closed. We will also pilot feasibility and acceptability of the intervention by completing provider surveys, semi-structured interviews with dental residents, and patient exit interviews.

4.2 Study Endpoints

4.2.1 Primary Study Endpoints

Feasibility will be assessed using provider surveys, semi-structured interviews, and EHR data.

Feasibility data collection.

We developed a checklist of 10 key components of the intervention based on process and will ask the dental resident and dentist subjects at the 6 FHC dental clinics if each was covered. Endorsement of 8 of the 10 checklist items (80%) by the dental provider subjects will be considered as the feasibility criterion. Specifically, we will estimate the average checklist endorsement score across all providers with its associated 95% confidence interval (CI); if the upper bound of the CI exceeds 80%, we will consider the process feasible.

Moreover, we will allow for open-ended collection of feedback on the feasibility of using the intraoral cameras for identification of oral lesions as part of the tele-mentoring intervention. Semi-structured interviews will also be conducted with dental resident subjects. We anticipate conducting 6 interviews before obtaining data saturation. The questions will be informed by the IOF and CFIR constructs and will assess specific barriers to sustaining the intervention and strategies for addressing those barriers to facilitate integration of the intervention into the routine workflow of the FHC dental clinics.

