4.2.2 Secondary Study Endpoints

Acceptability will be assessed using patient exit interviews (PEIs) conducted right after the dental visit is completed.

CONFIDENTIAL

This material is the property of the NYU School of Medicine and Langone Medical Center. Do not disclose or use except as authorized in writing by the study sponsor

Interventional Template Version: 28 APR 2017

Acceptability data collection.

Research staff will conduct a brief exit interview with 5 patients at each of the 6 FHC dental clinics with language interpretation services available regarding the acceptability of the intervention. We developed five statements on patient satisfaction with the intraoral cameras and the overall tele-mentoring intervention that will constitute the PEI. Patients will be asked the extent to which they agree with each statement (e.g., “Dentists should discuss with me ways to prevent and screen for oral cancer.”) (strongly agree, agree, disagree, strongly disagree). The acceptability criterion of the intervention will be that 80% or more of patients rate all five administered acceptability questions as “strongly agree” or “agree.” We will evaluate acceptability as described above for feasibility.

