5.6 Total Number of Subjects and Sites

All subjects will be recruited at the 6 FHC dental clinics in Brooklyn, NY.

The number of patient subjects will total 30 (5 from each of 6 FHC dental clinics).

The number of non-patient subjects will total 18: 12 dental resident and dentist subjects who will complete provider surveys (feasibility checklists), and 6 dental resident subjects who will complete semi-structured interviews.

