7.4 Safety Oversight

It is the responsibility of the Principal Investigator to oversee the safety of the study at her site. This safety monitoring will include careful assessment and appropriate reporting of adverse events as noted above, as well as the construction and implementation of a site data and safety-monitoring plan. Medical monitoring will include a regular assessment of the number and type of serious adverse events.

No DSMB will be convened for this pilot study.

8 Clinical Monitoring

Clinical site monitoring is conducted to ensure that the rights and well-being of human subjects are protected, that the reported trial data are accurate, complete, and verifiable, and that the conduct of the trial is in compliance with the currently approved protocol/amendment(s), with GCP, and with applicable regulatory requirement(s).

No independent clinical monitor will be assigned for this pilot study.

9 Statistical Considerations

Feasibility Data Analysis

Provider Survey. All quantitative analyses will be conducted by [name] under the direction of [name]. Endorsement of 8 of the 10 checklist items (80%) by the provider subjects will be considered as the feasibility criterion. Specifically, [name] will estimate the average checklist endorsement score across all dentists with its associated 95% confidence interval (CI); if the upper bound of the CI exceeds 80%, we will consider the process to be feasible.

Provider Semi-Structured Interview. All interviews will be transcribed by a transcription company and coded by 2 research staff members ([name] and [name]). The research staff members will code individually and then meet to discuss and agree upon the final codes. The analysis of the qualitative data will utilize the techniques of narrative analysis and be guided by the constant comparison analytic approach to identify themes.

Acceptability Data Analysis

Patient Exit Survey. The acceptability criterion of the intervention will be that 80% or more of patients rate all 5 administered acceptability questions as “strongly agree” or “agree” on a Likert Scale.

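### The 80% feasibility bar is tested with the upper confidence limit, so scores well below 80% can be declared feasible, and Section 4.2.2 appears to apply the same rule to acceptability

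*Combined protocol and SAP*

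**What the plan says.** **Feasibility (primary objective).** Section 4.2.1 states the bar: "Endorsement of 8 of the 10 checklist items (80%) by the dental provider subjects will be considered as the feasibility criterion". It then makes the bar operational through the average endorsement score across providers and its 95% confidence interval: "if the upper bound of the CI exceeds 80%, we will consider the process feasible". Section 9, under the provider survey analysis, gives the same rule: "if the upper bound of the CI exceeds 80%, we will consider the process to be feasible". Because it appears twice, it is unlikely to be a slip of the pen. Section 5.6 plans 12 completed checklists.

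**Acceptability (secondary objective).** Section 4.2.2 says "The acceptability criterion of the intervention will be that 80% or more of patients rate all five administered acceptability questions as" agree or strongly agree, and adds: "We will evaluate acceptability as described above for feasibility". Section 9 restates the bar, "The acceptability criterion of the intervention will be that 80% or more of patients rate all 5 administered acceptability questions", with no interval rule. Section 5.6 plans 30 patients, 5 per clinic.

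No section names the interval method, gives an expected SD, or describes the upper-limit rule as a deliberately lenient screen. Section 9.1 says that no sample size calculation is made.

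**The concern.** The criterion and the rule that implements it ask different questions. The criterion asks whether endorsement reached 80%. The rule asks whether the data are compatible with 80%. With 12 providers the interval is wide, so the two answers can differ by a large margin.

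The rule also rewards imprecision. For an observed average at or below 80%, more disagreement between providers, or fewer returned checklists, widens the interval and makes success easier.

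This is the only numeric decision rule for the primary objective; the interviews and EHR data have none. Section 3 makes scale-up of the program conditional on the pilot's success. A reader told that the 80% criterion was met could be looking at an average near 70%.

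**Working it through.** The plan contains no operating characteristic to reproduce, so the rule itself was evaluated.

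**Inputs.** From the documents: bar 80%; 95% interval, taken as two-sided; 12 providers with 10 items each; 30 patients. Assumed, because the documents are silent: interval method and between-provider SD.

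**Feasibility: lowest passing average, t interval.** The cutoff is 80 − t(0.975, 11) × SD/√12, with t = 2.201.

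- SD 10: 80 − 6.35 = 73.6%
- SD 15: 80 − 9.53 = 70.5%
- SD 20: 80 − 12.71 = 67.3%
- SD 25: 80 − 15.88 = 64.1%

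A small SD of 5 points still gives 76.8%. At SD 20, if only 6 checklists came back, the cutoff would fall from 67.3% to 59.0%.

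**Feasibility: a different interval.** Pooling the 120 item responses and using a binomial interval, the lowest passing count is 87/120 = 72.5% (Clopper–Pearson upper limit 80.25%) or 88/120 = 73.3% (Wilson 80.4%). The problem does not depend on the t interval.

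**Two worked cases (t interval).**

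- Scores 4, 5, 5, 6, 6, 7, 7, 8, 8, 9, 9, 10: mean 84/12 = 7.0, or 70%; SD 18.6 points; half-width 2.201 × 18.6/√12 = 11.8; interval 58.2 to 81.8%. Only 5 of 12 providers reach 8 items, yet the rule returns feasible.
- All 12 providers endorse exactly 8 items: SD 0, upper limit 80.0%, which does not exceed 80%. The rule returns not feasible although the criterion is met.

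**Chance of declaring feasibility.** Beta-binomial simulation of 12 independent providers with 10 items each, at least 200,000 replicates, with correlation ρ among items within a provider of 0, 0.1 or 0.2. The implied SD in points is 100 × √[p(1 − p)(1 + 9ρ)/10]; at p = 0.70 this is 14.5, 20.0 and 24.2.

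| True average | Upper-limit rule, t interval, % (ρ = 0 / 0.1 / 0.2) | Upper-limit rule, pooled Clopper–Pearson, % (range over ρ) | Observed average at least 80%, % (ρ = 0 / 0.1 / 0.2) |
|---|---|---|---|
| 65% | 10.7 / 38.0 / 57.2 | 5–17 | 0.0 / 0.5 / 1.8 |
| 70% | 42.3 / 69.2 / 80.8 | 31–40 | 0.9 / 4.4 / 8.0 |
| 75% | 82.1 / 91.3 / 94.5 | 68–77 | 12.2 / 20.4 / 25.3 |
| 80% | 98.4 / 98.9 / 99.2 | 90–98 | 55.4 / 54.9 / 54.8 |

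**Acceptability, if Section 4.2.2 imports the upper-limit rule.** The stated bar is 0.80 × 30 = 24 patients. The smallest count whose upper limit exceeds 80% is 19/30 = 63.3% (Clopper–Pearson 80.07%, Wald 80.6%) or 20/30 = 66.7% (Wilson 80.8%). No SD is needed. Exact binomial chance of passing, patients taken as independent:

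| True proportion | 19 or more, % | 20 or more, % | 24 or more, % |
|---|---|---|---|
| 70% | 84.1 | 73.0 | 16.0 |
| 75% | 94.9 | 89.4 | 34.8 |
| 80% | 99.1 | 97.4 | 60.7 |

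A result of 20 to 23 of 30 would therefore pass under Section 4.2.2, so read, and fail under Section 9.

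**The case against.** The best defense is that this is a one-year, minimal-risk pilot with no comparison between groups. Not ruling out the target is a coherent pre-specified screen for a small sample, and judging on the observed value has its own cost: at a true average of exactly 80% it fails about 45% of the time. Feasibility also draws on interviews and EHR data, and the average and its interval are to be estimated in any case. This would carry weight if the plan called the rule a lenient screen. It does not; it presents the rule as the way the 80% criterion is applied.

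Three qualifications stand:

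- Only a band of averages below 80% passes, and its width depends on an SD and a method that the plan does not give. The highest pass chances need the t interval and substantial correlation among items.
- The cross-reference in Section 4.2.2 could mean only that an estimate and interval will be produced. The upper-limit reading is the natural one, but the acceptability figures are conditional on it.
- The six-checklist case is hypothetical; Section 7.1.1 plans two respondents at each of six clinics.

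None of these removes the mismatch between criterion and rule.

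**Conclusion.** The concern holds, and the rule should be changed before the data are analyzed. As written, the decision rule for the primary objective does not test the plan's own 80% criterion. Under a t interval with SDs of 10 to 25 points, averages just above 64.1 to 73.6% would be declared feasible; pooled binomial intervals put the cutoff at 72.5 to 73.3%. At a true average of 70%, the chance of a positive declaration is 42 to 81% (t) or 31 to 40% (pooled Clopper–Pearson), against 1 to 8% when the observed average must reach 80%.

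For acceptability, on the natural reading of Section 4.2.2, the bar drops from 24 to 19 or 20 of 30. Whichever reading was meant, Sections 4.2.2 and 9 need to be reconciled.

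The calculations ignore clustering by clinic. Positive within-clinic correlation would widen a correct interval and make the upper-limit rule more lenient still.

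**What to change.** In Sections 4.2.1 and 9, use one rule: *The process will be considered feasible if the mean checklist endorsement score across all surveyed providers is at least 80%; the two-sided 95% confidence interval will be reported to show precision.* While editing, settle who is averaged, since Section 4.2.1 refers to providers and Section 9 to dentists.

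In Sections 4.2.2 and 9: *Acceptability is met if the observed proportion of patients answering agree or strongly agree to all five questions is at least 80%; its 95% confidence interval will be reported.* Name both interval methods in Section 9.

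If a not-ruled-out screen was intended, the alternative is to say so, justify it, state it identically in all three sections, and not describe a pass as meeting the 80% criterion. Requiring the lower limit to exceed 80% is not recommended at these sample sizes: it would need an average above 86.4, 89.5 or 92.7% at SD 10, 15 or 20, and 28 or 29 of 30 patients.

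The cost is one or two sentences per section, with no new data or subjects. Success becomes harder to declare: at a true value of exactly 80%, the chance falls to about 55% for feasibility (from 98–99% with a t interval, or 90–98% with pooled Clopper–Pearson) and to about 61% for acceptability (from 97–99%).
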